# 5.6 Randomisation

Online randomisation system provided by the Mental Health and Neurosciences Clinical Trials Unit, King's College London. Recruits will be randomly allocated in a 1:1 ratio to standard TUS removal (cystoscopic removal at 6 weeks) and early TUS removal (on day 5 with catheter). Randomisation type is stratified block randomisation with randomly varying block sizes. Stratification is for age - adult or child.

#### 5.7 Study Objectives

#### **Primary Objective**

To determine the effect of early TUS removal on the incidence of stent related complications (namely pain, haematuria, urinary tract infection, migration and fragmentation)

#### **Secondary Objectives**

To determine the effects of early TUS removal by attaching the stent to catheter on:

- 1. ureteric complication rates
- 2. patient acceptability
- 3. procedural costs
- 4. resource availability and allocation

# 5.8 Study Endpoints

#### Primary Endpoint

Incidence of stent related complications (composite endpoint) in each arm

#### **Secondary Endpoints**

- 1) Incidence of ureteric leak at 3months post transplantation for each arm
- 2) Incidence of ureteric stenosis at 6 months post transplantation for each arm
- 3) Quality of life assessment using FAIT-U and EQ-5D at week 1 and week 6 post transplant
- 4) Patient completed diary cards (day of stent removal)
- 5) NHS reference costs for stent removal procedure and management of stent related complications at 6 months.

# 5.9 Trial Treatments

The study is a randomised control trial in which there are two potential study arms to which patients are randomly allocated, see below. It is not possible to blind patients or investigators as to whether they will undergo the standard technique or the novel technique for stent removal due to noticeable differences in the method of procedure.

*Group 1*: CONTROL - Standard technique for TUS removal (sTUSr) *Group 2*: TRIAL - Novel technique with early TUS removal (eTUSr)

A TUS is placed at the time of surgery along with a urinary catheter in all patients. Patients in Group 1 will have the urinary catheter removed on the ward on the 5th post-operative day. They will then undergo a cystoscopy, under either local or general anaesthetic, at week 6 to remove the TUS. Cystoscopy and stent removal takes

approximately 10 minutes. Patients will be given a prophylactic intravenous injection of antibiotic to cover the procedure. Patients in Group 2 will have the TUS attached to the urinary catheter at the time of surgery. These patients will have the urinary catheter removed on the ward on the 5th post-operative day in the standard way. As the TUS is attached to the catheter it will be removed at the same time as removal of the catheter. Catheter removal simply involves deflating the catheter balloon to allow it to slide out from the bladder. It is a non-invasive procedure that does not cause discomfort or risk to the patient. Removing the catheter with the stent attached will not change this. Group 2 therefore do not require cystoscopy.

The study will be performed prospectively. Patients that require kidney transplantation will be recruited and allocated to a study arm. Participants of the study will have routine clinical follow up in the same way as non-participants. A diary card will be completed by both trial groups on the day of their stent removal. Stent related symptom assessment and quality of life questionnaires will be completed by all adult participants at week 1 and week 6. Data will be collected on all participants regarding ureteric complications, stent related complications, health economics and patient quality of life assessments for 3 months post transplantation. Complications of ureteric stenosis will monitored for up to 6 months post transplantation.

# 5.10 Surgical Technique

All surgeons perform the transplant ureter / bladder anastomosis using an extra-vesical technique (modified Lich-Gregoir Technique). All patients have a double J stent (Cook Medical) and a urethral catheter inserted. It is advantageous but not essential to tape the external section of the bladder catheter to the patient's thigh to maintain its position in the bladder to increase ease of locating the catheter tip intra-operatively.

In patients randomised to eTUSr the ureteric stent will be attached to the "eye" of the urethral catheter. This should be done by passing the "string" attached to the stent through the "eye" of the urethral catheter and tying a knot to secure the "string" to the catheter. An acceptable alternative is to pass a non-absorbable suture through both the lower end of the stent and the "eye" of the urethral catheter.

# 5.11 Cystoscopic Stent Removal

All patients will have urine dipstick testing and MSU sent for MC&S prior to cystoscopic stent removal. For patients without UTI symptoms and with a normal urine dipstick result cystoscopy should be covered with a single dose antibiotic chosen according to local practice.

Where either there is a positive dipstick for nitrites or the presence of UTI symptoms the following possible scenarios are all acceptable:

- Lower urinary tract symptoms but dipstick test is nitrite negative proceed as above but may also require oral antibiotics post procedure for 3-5 days (follow local guidelines for antibiotic prescribing).
- Dipstick positive for nitrites +/- lower urinary tract symptoms, but no systemic features - proceed to stent removal with antibiotic cover as above. Oral antibiotics may also be prescribed post procedure for 3-5 days (follow local guidelines for antibiotic prescribing).

- Dipstick positive & upper urinary tract symptoms or systemic features of infection consideration of delaying stent removal for up to 48 hours to permit antibiotic treatment for 48 hours prior to proceeding with stent removal The procedure should be covered with appropriate antibiotics and antibiotics continued for a further 7 14 days.
- If there is a prior positive culture on MSU antibiotics may also be prescribed prior to stent removal and continued post procedure for 3-5 days.

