# 7.1 TUS-related complication definitions:

Complications are defined as occurring in first 3 months post transplant except transplant ureteric stenosis which can develop insidiously and so will be recorded for the first 6 months post transplant.

- Urinary Tract Infection (UTI) microbiology (MC&S) in the early (<3month) post transplant setting
  - Symptomatic dysuria / fever / pain over transplant or native kidneys with Mid Stream Urine (MSU) culture bacteria  $> 10^{x^2}$  with pyuria
  - Asymptomatic Mid Stream Urine (MSU) culture bacteria  $> 10^{x5}$  with pyuria
- Stent migration ultrasound and / or plain x-ray diagnosis of TUS not appropriately positioned (coils not in both the transplant renal pelvis and the bladder).
- Stent pain requiring stent removal
- Haematuria frank haematuria requiring catheterisation +/- irrigation
- Stent Fragmentation

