#### 7.2 Follow-up schedules and requirements

Patients in the eTUSr group who have urethral catheter / stent removed earlier or later than Day 5 post operation will have the reason clearly documented in medical notes. The post-operative day urethral catheter / stent removed will be clearly recorded. Patients in the sTUSr group will have the TUS removed in week 6 post transplant. Patients who have TUS-related complications that warrant TUS removal before 6 weeks will have the reason clearly documented in medical notes. The post-operative day the TUS is removed will be clearly recorded. If for administrative reasons (such as availability of cystoscopy list) TUS removal is earlier or later than 6 weeks the reason clearly documented in medical notes.

Urine samples will be collected routinely (current clinical practice) as follows:

- At admission for transplant: in patients who pass urine MSU for MC&S (microscopy, culture and sensitivity)
- Prior to urethral catheter removal day 5 CSU (catheter specimen urine) for MC&S
- At each transplant outpatient clinic midstream urine samples are dipstick tested. Abnormal results on dipstick test are sent for MC&S. Month 1: 3 visits/ week; Month 2: 2 visits/ week; Month 3: 1 visit / week.

• Prior to cystoscopic removal of TUS - MSU for dipstick and MC&S (microscopy, culture and sensitivity)

Health economics:

- Assessment of costs of eTUSr versus sTUSr.
  - Hospital costs assessed by NHS reference costs.
  - Patient costs by self-completed diary cards and will include both direct costs (expenditure) and indirect costs (e.g. loss income).

Patient satisfaction:

• Quality of Life assessment (using FAIT-U, version 4.0 and EQ -5D) will be carried out by adult participants in both treatment arms.

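### Controls alone have a urine culture at week 6 whatever the dipstick shows, and an asymptomatic positive counts in the primary endpoint, so detection is tilted towards early removal

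*Protocol*

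**What the plan says.** **Culture before cystoscopy.** Protocol 5.11 orders: "All patients will have urine dipstick testing and MSU sent for MC&S prior to cystoscopic stent removal". The urine schedule in 7.2 repeats this. The culture does not depend on the dipstick result.

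**Who has it, and when.** On timing, 7.2 says: "Patients in the sTUSr group will have the TUS removed in week 6 post transplant". Of the early-removal arm, 5.9 says: "Group 2 therefore do not require cystoscopy". No week-6 culture is scheduled for that arm.

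**Clinic samples, both arms.** Midstream samples are dipstick tested at each visit, and "Abnormal results on dipstick test are sent for MC&S". The visit schedule is "Month 1: 3 visits/ week; Month 2: 2 visits/ week; Month 3: 1 visit / week".

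**Other cultures without a dipstick condition.** Section 7.2 lists a midstream sample at admission, in patients who pass urine, and at day 5: "Prior to urethral catheter removal day 5 CSU (catheter specimen urine) for MC&S". Both apply equally to the two arms.

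**What counts.** The UTI definition in 7.1 has a symptomatic branch and an asymptomatic one, the latter beginning "Asymptomatic Mid Stream Urine (MSU) culture bacteria" and requiring a higher colony count together with pyuria. The window is the first 3 months after transplant. Sections 5.7 and 5.8 make UTI part of the composite primary endpoint. Nothing excludes the pre-cystoscopy sample from it.

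**The concern.** An endpoint that depends on testing is comparable between arms only if testing is comparable. Here one arm has an additional culture inside the endpoint window, and a positive result without symptoms is enough for an event. An extra test can add counted events but cannot remove any, so the bias has one direction: it raises the control rate and makes early removal look better.

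Randomisation does not protect against this, because the difference arises in measurement after allocation. Nor does the age-stratified Mantel-Haenszel test in section 7. A larger trial does not help either: moving from 176 to 320 patients makes a fixed artefact easier to declare significant. UTI is the component that matters most, since section 5.5 says the audited complications are mainly UTI.

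**Working it through.** **1. Scheduled cultures by arm (Protocol 5.9, 5.11, 7.2)**

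| Sample | Early removal | Standard removal | Depends on dipstick? |
|---|---|---|---|
| Admission midstream sample | yes | yes | no |
| Day-5 catheter specimen | yes | yes | no |
| Clinic midstream samples to 3 months | yes | yes | yes, only if abnormal |
| Midstream sample before week-6 cystoscopy | none | yes | no |

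Only the last row differs. The first two are identical in both arms and do not offset it. In addition, the admission sample precedes the transplant complications being counted, and the day-5 sample is a catheter specimen, whereas the UTI definition is written for midstream urine.

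**2. The plan's own figures**

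Inputs (5.5): 20% or 15% against 5%, two-sided 5%, 80% power, chi-squared test.

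Formula: n = [1.960·√(2p̄(1−p̄)) + 0.842·√(p1(1−p1)+p2(1−p2))]² / d², then with continuity correction n′ = (n/4)·[1+√(1+4/(nd))]².

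- 20% v 5%: p̄ = 0.125, d = 0.15; n = 75.1 (76 rounded up); n′ = 87.9, so 88.
- 15% v 5%: p̄ = 0.10, d = 0.10; n = 140.1 (141 rounded up); n′ = 159.5, so 160.

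Both stated sizes reproduce with the continuity correction. The sample size is not in error; the issue is ascertainment.

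**3. Effect of the extra culture when there is no true difference**

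The protocol gives no yield for dipstick-normal positive cultures. Let q be the assumed share of otherwise event-free controls who are counted only through this culture. With the same true rate p in both arms, the observed control rate is p + (1−p)q. Using q among event-free patients avoids counting anyone twice.

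At p = 15%, the lower end of the audited 15 to 20%, the control rate for q = 1, 2, 3 and 5% is 0.15 + 0.85q = 15.85, 16.70, 17.55 and 19.25%. The artefact is thus 0.85, 1.70, 2.55 and 4.25 percentage points, against a planned difference of 10 points (15% to 5%).

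The rejection probability comes from exact enumeration of two binomials with the uncorrected, unstratified chi-squared test at two-sided 5%. The probability of a significant result favouring early removal is in brackets.

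| q (assumed) | 88 per group | 160 per group |
|---|---|---|
| 0 | 4.9% (2.4%) | 4.9% (2.5%) |
| 1% | 5.1% (3.4%) | 5.4% (3.9%) |
| 2% | 5.9% (4.8%) | 6.9% (6.0%) |
| 3% | 7.2% (6.4%) | 9.3% (8.8%) |
| 5% | 11.3% (11.0%) | 17.0% (16.8%) |

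At p = 20%, the upper end of the audit, the two-sided rates for q = 1, 2, 3 and 5% are 5.2, 5.8, 6.8 and 9.9% at 88 per group, and 5.3, 6.4, 8.2 and 13.9% at 160 per group.

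The stratified Mantel-Haenszel test itself was not modelled. A continuity-corrected test is more conservative: at p = 15% and 88 per group it rejects 3.0% of the time with no artefact, and 4.2 to 5.6% with an added 2 to 3 points.

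**The case against.** The best counter-argument is that the extra yield must be small. An asymptomatic UTI needs a high colony count and pyuria, and pyuria makes a wholly normal dipstick less likely. Both arms are dipstick tested often: taking four weeks to a month, 3×4 + 2×4 + 1×4 = 24 visits, two a week around week 6. Any abnormal result is cultured, in either arm. What remains is the asymptomatic, dipstick-normal control who has both pyuria and a high count at that one visit and no other complication in 3 months. The sample is also part of current clinical practice. All of this stands, and it is why the size is left open. At q = 1% the false-positive rate is close to nominal. None of it removes the asymmetry or its direction.

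Three stronger readings are tempting but unsupported:

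- *That controls alone are ever cultured without a dipstick trigger.* The admission and day-5 samples are unconditional in both arms; the difference is the week-6 sample only.
- *That a stent in place makes dipsticks abnormal, and so generates further control cultures.* The protocol does not say so. The haematuria it lists as a complication is frank bleeding requiring catheterisation, not a dipstick finding.
- *That the false-positive rate reaches about 17% at 88 per group and 27% at 160.* Those values need a 10% true rate, which appears nowhere in the protocol, and a full 5-point gain, the top of an assumed range.

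**Conclusion.** The point holds as an ascertainment bias of known direction and unknown size. Followed as written, the protocol gives controls one additional culture inside the 3-month window and lets an asymptomatic positive count in the primary composite. The bias favours early removal and affects the estimate even where it does not change the test result.

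The size rests on two assumptions: a yield of 1 to 5% among otherwise event-free controls, and a common true rate of 15%. On those, the two-sided error rate runs from almost nominal (5.1% at 88 per group) to 17.0% (160 per group), nearly all of the excess in favour of early removal. The documents cannot place the trial within that range. The change is still worth making, because it costs very little and the trial is open-label: a decision taken after results are known about which cultures count would be open to challenge.

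**What to change.** **Preferred: one sentence in section 7.1.** State that an asymptomatic UTI found only by the pre-cystoscopy culture, with a normal dipstick on that sample, does not count in the primary endpoint and is reported separately, with a sensitivity analysis that includes it. Define a normal dipstick as one that would not have been sent for culture under the clinic rule in 7.2, because 5.11 sorts its scenarios largely by nitrites whereas 7.2 refers to any abnormal result. Cultures scheduled identically in both arms are unaffected.

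Cost: slightly fewer control events, some of them genuine bacteriuria. No new sample is needed, since 5.11 already requires a dipstick at that visit, but its result must be recorded in the trial data. Controls would still have one more dipstick than early-removal patients, a small residual imbalance.

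**Alternative: equal sampling.** For endpoint ascertainment, send one midstream sample for culture from each early-removal patient at a week-6 clinic visit already in the schedule. This loses no events and makes the arms match, at the cost of one routine culture per early-removal patient. It must be in place before those visits occur, because an analysis plan cannot later supply samples that were never taken.

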# 6. EXPERIMENTS/LABORATORY TESTS

#### 6.1 Microbiology Experiments

This study provides a unique opportunity to link "state of the art" molecular diagnostics of infection with the potential to increase our knowledge of urinary tract infection in this setting. A subset of transplant ureteric stents from each group, once removed from the patient, will be analysed by confocal laser microscopy to assess for bacteria in patients both with and without defined urinary tract infection. The stents will be orientated and differences in the bacteria (number or type) in the proximal (kidney) versus distal (bladder) ends will be assessed. Biofilms will be quantified by confocal microscopy  using Dead/Live stain (Molecular Probes) and the presence and distribution of specific pathogens especially Enterococcus faecalis  will be determined using species-specific probes with fluorescent in situ hybridization (FISH).

These molecular techniques will provide an additional level of information relating to TUS infection. They will permit comparison to standard urine culture and assess whether there are particular sites on the stents that bacteria tend to colonise. This work will be conducted in collaboration with [name], King's College London, using the core imaging facilities of KCL. Descriptive statistics and estimates of differences between groups will be determined with 95% confidence intervals.

# 7. DATA ANALYSIS

The primary outcome is stent related complication rates and the two study arms will be compared against each other. For the primary end-points a stratified Mantel-Haenszel test will be used. The secondary outcomes are: ureteric complication rates, economic costs, stent related symptoms and quality of life scores. For secondary endpoints analysis of covariance will be used for continuous endpoints, unless there is evidence that the assumption of normality is untenable in which case a stratified Wilcoxon test will be used. For dichotomous data a stratified Mantel-Haenszel test will be used.

Each treatment arm will be considered in terms of costs divided by quality-adjusted life year (QALY) and also incremental cost effectiveness ratio (ICER). QALYs will be derived from facit (FAIT-U) and EQ-5D questionnaires. Health economic evaluations will be made in collaboration with [name], London School of Economics.

All analyses will be stratified by age. Given our patient population for the study (see below) we will stratify randomisation into paediatric (less than 16 years old) and adult populations. As urinary tract causes of renal failure are higher (~25%) in children

compared with adults (~ 5%), this stratification will also cover the majority of patients at higher risk of UTI.

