# Potential Benefits:

To patients: No need for a cystoscopy for stent removal. Patients are keen to avoid a second procedure (cystoscopy) for stent removal, as shown by a questionnaire carried out in our centre. With no required cystoscopy, patients and their relatives should benefit from reduced travel costs, work related problems, loss of income and time. To patients and hospital: early stent removal with the new technique should decrease the

incidence of stent related problems, especially urinary tract infection. This may decrease need for antibiotics, risk of antibiotic resistance and hospital admissions.

To hospital: The cost of outpatient flexible cystoscopy under local anaesthetic is around  $\pounds$ 766 per patient. Costs when general anaesthetic is required are considerably higher. This method will potentially free-up flexible cystoscopy resources to improve access for other patients requiring urgent diagnostic cystoscopy for bladder cancer.

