# 4. TRIAL OBJECTIVES

The study has 4 main objectives:

1) To determine if early transplant ureteric stent removal (eTUSr) leads to a decrease in stent related complications

2) To determine the effect of eTUSr on ureteric complication rates (ureteric leak or stenosis)

3) To determine if eTUSr results in better patient acceptability

4) To determine if eTUSr leads to improved cost effectiveness

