#### 8.2 Potential risks

There is the potential for unexpected complications in the new technique arm of the study. These may be related to the early removal of the stent on the 5th post operative day.

- The main potential complication is an increase in the urinary leak rate (>1%). This would be clinically detectable by a decrease in voided urine volume and discomfort around the transplanted kidney. Investigation would be with an ultrasound scan. Treatment would be with replacement of the urinary catheter for 2 weeks and a cystogram before removal. Any incident of urinary leak in either group would be immediately reported to the Trial Data Safety Monitoring Committee. An increase incidence in urinary leak rates (>2 cases in the first month) in either arm would trigger a trial safety review and if necessary temporary cessation in the study until appropriate clinical review. However, data to date from the literature  and personal communications (The Mayo Clinic, 2006) suggest no increase in urinary leak complication rate with the new technique.
- There is the potential that we find an increase rate (>15-20%) of ureteric stenosis in the early (3 month) post transplant period. This would present with a decrease in void volume, discomfort around the transplant or deteriorating renal function.

Investigation would involve an ultrasound scan and be initially managed with either nephrostomy or retrograde insertion of ureteric stent. Nephrostogram / retrograde x-ray would be obtained to confirm diagnosis. Treatment would involve either endo-urological or an open corrective surgical approach. >3 cases of stenosis in the first 3 months would generate trial review. Data to date does not suggest increased complications of stenosis with early removal of ureteric stents.

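### Costs divided by QALYs within each arm is not a valid basis for comparing the arms, and a bare ICER may be hard to read when a saving is expected

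*Protocol*

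**What the plan says.** Protocol Section 4 lists cost effectiveness as the fourth of four main objectives: "To determine if eTUSr leads to improved cost effectiveness". Section 7 (Data Analysis) names the summaries: "Each treatment arm will be considered in terms of costs divided by quality-adjusted life year (QALY) and also incremental cost effectiveness ratio (ICER"). It then gives the source of the QALYs: "QALYs will be derived from facit (FAIT-U) and EQ-5D questionnaires".

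The expected saving is in Section 3, Potential Benefits: "The cost of outpatient flexible cystoscopy under local anaesthetic is around" GBP 766 per patient, and more under general anaesthetic. Section 5.9 explains why it arises: "Group 2 therefore do not require cystoscopy". Section 3 also hopes for less infection-related care: "This may decrease need for antibiotics, risk of antibiotic resistance and hospital admissions". The cost endpoint in Section 5.8 is "NHS reference costs for stent removal procedure and management of stent related complications at 6 months", while EQ-5D and FAIT-U are collected at weeks 1 and 6. Section 8.2 names urinary leak and ureteric stenosis as potential risks of the new technique.

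**The concern.** A choice between two arms turns on the difference in cost set against the difference in QALYs. A per-arm ratio divides by all the QALYs a patient accrues, most of which have nothing to do with how the stent is removed. Whether it notices a QALY loss therefore depends on the background level of cost and QALYs, which is irrelevant to the choice. The case that matters is a cheaper arm with fewer QALYs. Section 8.2 makes that conceivable, because leak or stenosis could follow early removal.

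The ICER raises a lesser issue. With a saving expected, it may be negative, and the same negative number arises when eTUSr dominates and when it is dominated.

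The QALY source is also unclear. Sections 5.8 and 7.2 use FAIT-U as a quality-of-life questionnaire, and the protocol gives no utility weighting for it and no rule for combining it with EQ-5D.

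**Working it through.** The protocol states no cost-effectiveness result or threshold, so there is no economic figure to reproduce.

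**Inputs.** From the protocol: S = GBP 766 (Section 3). Assumed, because the protocol does not give them: control cost C = GBP 1,000 to 20,000 per patient; control QALYs Q = 0.30 to 0.40 over 6 months; willingness to pay λ = GBP 20,000 to 30,000 per QALY.

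**Switch points.** Let eTUSr save S and lose L QALYs.

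- The average ratio favours eTUSr while (C − S)/(Q − L) < C/Q, that is, while L < Q×S/C.
- Incremental net benefit, S − λL, favours eTUSr while L < S/λ.
- The two limits coincide only if C/Q = λ.

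Net benefit switches at 766/20,000 = 0.0383 or 766/30,000 = 0.0255, whatever C and Q are. The average ratio switches between 0.30×766/20,000 = 0.0115 and 0.40×766/1,000 = 0.306.

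**Disagreement in both directions (Q = 0.35).**

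| | C = 1,500, L = 0.05 | C = 20,000, L = 0.02 |
|---|---|---|
| Control ratio | 1,500/0.35 = 4,286 | 20,000/0.35 = 57,143 |
| eTUSr ratio | 734/0.30 = 2,447 | 19,234/0.33 = 58,285 |
| Ratio favours | eTUSr | control |
| Net benefit, λ = 20,000 | 766 − 1,000 = −234 | 766 − 400 = +366 |
| Net benefit, λ = 30,000 | 766 − 1,500 = −734 | 766 − 600 = +166 |
| Net benefit favours | control | eTUSr |

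**Shorter horizon.** If QALYs cover only about 6 weeks (assume Q = 0.08), the ratio switches at 0.08×766/1,500 = 0.041, 0.08×766/5,000 = 0.012 or 0.08×766/20,000 = 0.003. The net benefit limits are unchanged, so disagreement remains possible.

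**Where the ratio is safe.** If eTUSr saves money and gains g ≥ 0 QALYs, (C − S)/(Q + g) is always below C/Q, so the ranking is right.

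**ICER.** A saving of 766 with a gain of 0.01 gives −766/0.01 = −76,600. An extra cost of 766 with a loss of 0.01 gives 766/−0.01 = −76,600. At λ = 20,000 the net benefits are 200 + 766 = +966 and −200 − 766 = −966. Positive values share the problem: (−766, −0.05) and (+766, +0.05) both give 15,320, with net benefits of −234 and +234.

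**The case against.** The other side has a good deal to say, and much of it stands.

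- **No ranking rule is stated.** A reader might infer that the arms are to be scored or chosen by the per-arm ratio. Section 7 says only that each arm is considered in those terms, alongside an ICER. The point is therefore that the ratio should not serve as a comparative summary, not that a wrong decision rule has been adopted.
- **The ICER is standard.** Whoever computes it has both differences and knows the quadrant. Thresholds, dominance rules and net benefit are commonly left to an analysis plan, so their absence from the protocol is no finding. What remains is a presentational weakness of the bare number.
- **Part of the comparison is already planned.** Section 7 lists economic costs and quality-of-life scores as secondary outcomes, with analysis of covariance for continuous endpoints. That covers costs, but not QALYs or the two jointly.
- **A built-in bias towards eTUSr is not shown.** A reader might infer that removing the cystoscopy makes the ratio nearly bound to favour eTUSr. The second column of the table shows the opposite error. Treating leak or stenosis would also erode the saving.
- **The losses needed are large.** A mean loss of 0.0383 QALY is a utility fall of 0.0383/0.5 = 0.077 in every eTUSr patient for 6 months, or 0.0383/(6/52) = 0.33 over 6 weeks. The illustrated 0.05 needs 0.10 or 0.43. By contrast, a 2% leak rate with all utility lost for the 2 weeks of catheterisation in Section 8.2 costs 0.02×2/52 = 0.0008 QALY. Stenosis at the 20% level in Section 8.4 would need a fall of 0.0383/(0.20×0.5) = 0.38 for 6 months in each affected patient. This limits the likelihood of misranking in the low-cost case, not the principle.
- **FAIT-U.** A reader might infer two competing QALY values per patient. The sentence can be read that way but does not say so; the text supports only that the QALY source is ambiguous.

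**Conclusion.** The concern holds in limited form. Section 7 fixes a per-arm costs-to-QALY summary for a main objective, and that summary is not a valid basis for comparing arms. It can disagree with incremental net benefit in either direction when the cheaper arm has fewer QALYs (or the dearer arm more), and it ranks correctly when eTUSr is cheaper and no worse. The disagreement follows from algebra. Its size does not come from the protocol: only the GBP 766 is stated, and C, Q and λ are assumptions, so the figures are illustrative. The ICER is acceptable if its quadrant is shown. The QALY source needs one instrument named. The point is minor to moderate, on a secondary economic analysis; the primary comparison and the sample size are untouched.

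**What to change.** In Section 7, drop costs divided by QALYs in each arm as a comparative summary. Report instead the between-arm differences in mean cost and in mean QALYs, each with a 95% confidence interval, and the incremental net monetary benefit over a stated range of willingness-to-pay values. Report an ICER only when neither arm dominates, and name the quadrant. Derive QALYs from EQ-5D and report FAIT-U as a separate symptom and quality-of-life score.

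This takes one or two sentences and no new data. The cost is that a willingness-to-pay range must be stated and the simple per-arm figure is lost.
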